  - i. Study Design 1: collect all urine for the first 24 hours in the PCRU. Discharge participant with urine jug at 24 hour and 48 hour time point and instruct participants to return urine jug 24 hours later to PCRU. Record volume of urine excreted for the intervals of 0-24 hrs, 24-48 hrs, and 48-72 hours post drug administration. Collect a ~10 mL sample from each urine interval. NB: The study team will instruct the participant that every attempt should be made to collect all urine, however the team recognizes that collecting urine while at school or at work may not be feasible.
  - ii. Study Design 2: collect all urine 12 hours post drug administration. Record the volume of urine excreted. Collect a ~10 mL sample.
- p. Collect ~ 2 mL of saliva. Instruct participant not to eat or drink for 30 minutes prior to beginning to spit.
- q. Remove sweat patches
  - i. For Study Design 1, remove one sweat patch 12 and 24 hours post drug administration. Place sweat patch in labeled ziplock bag for storage at -70°C until analysis.

- ii.* For Study Design 2, remove one sweat patch 8 and 12 hours post drug administration. Place sweat patch in labeled ziplock bag for storage at -70°C until analysis.
- r. The research team will ask the participant to fast for 2 hours after drug administration. After this 2-hour mark, the participant is free to eat and drink as desired. Document all meal times and content. Collect food receipts when available. The following are scenarios where the research team may deviate from fasting for 2 hours post-administration:
  - i.* A participant may request to take atomoxetine with a small amount of soft food (e.g., pudding, applesauce, etc.) to aid with capsule swallowing. Document the food and approximate volume the participant used to aid with capsule swallowing (e.g., participant took capsule with ~1 teaspoon of chocolate pudding).
  - ii.* If participant reports GI upset, a small snack may be given to alleviate symptoms, even in the event that the fasting time has not been completed. Document GI upset as an adverse event in the adverse events log. If snack is given, document the snack time and content.
- s. Perform assessment of attention tasks (Pupillometry during Posner's Cuing Task). Further details can be found in Appendix H.

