Estimation of the pharmacodynamics parameters and generation of statistical analyses will be performed by The Division of Clinical Pharmacology, Toxicology & Therapeutic Innovation at the Children's Mercy Hospital, Kansas City, MO. An indirect model of pharmacodynamic changes, using change in plasma DHPG as a function of systemic plasma ATX concentration will be evaluated using Phoenix NLME (Certara, Princeton, NJ, USA), NONMEM (Icon, Dublin, Ireland), MATLAB (Natick, MA, USA), SAS version 9.4 (SAS, Cary, NC, USA), and R (The R Foundation). Concentration changes in DHPG as a function of change in systemic ATX levels will be fit to an indirect model (Equation A). Pharmacodynamic parameters  $k_{in}$ ,  $k_{out}$ ,  $I_{max}$ , and  $IC_{50}$  will be estimated for each metabolite studied using a nonlinear mixed effects model to take into account variability of pharmacodynamic marker change within the study population. Statistical regression models will be constructed to determine which patient covariates are

predictive of pharmacodynamic response. A maximal effect ( $E_{max}$ ) model describing the relationship between ATX concentration and pharmacodynamic effect will also be assessed in this study (Equations B and C). Models will be compared using statistical tests (Sum of Squares, Loglikelihood, AIC, standard error of estimates, and distribution of residuals). Changes in ATX  $C_{max}$  and  $AUC_{0-\infty}$  will also be plotted against pupillometry and eye-tracking data gathered when testing participants with localization and discrimination tasks. To describe the relationship between attentional orientating as function of ATX exposure, the data will be regressed both linearly and non-linearly and best of fit statistics (Akaike Information Criteria and Bayesian Information Criteria) will be employed to determine the most appropriate model.

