#### *Global Neurotransmitter Analysis*

$k_{in, DHPG}$	Rate at which DHPG is created endogenously
$k_{out, DHPG}$	Rate at which DHPG is catabolized endogenously
$I_{max, DHPG}$	Maximal fractional inhibition produced by ATX
$IC_{50, DHPG}$	Concentration of ATX that results in 50% of maximal inhibition
$E_{max, DHPG}$	Maximum response through interaction of drug and drug target
$EC_{50, DHPG}$	Concentration of ATX that results in 50% of maximal response

Rates of formation and elimination ( $k_{in}$  and  $k_{out}$ ), maximal inhibition ( $I_{max}$ ), concentration at which 50% maximal inhibition is achieved ( $IC_{50}$ ), maximal response ( $E_{max}$ ), and concentration at which 50% maximal response is achieved ( $EC_{50}$ ) will be determined for all neurotransmitters assessed in the global neurotransmitter panel (see Appendix I for metabolite list). The Dietary Survey Questionnaire and microbiome information from saliva samples will be analyzed as possible covariates of the neurotransmitter profiles.

**Genetic Analysis:** Genome-wide analysis and single nucleotide polymorphism (SNP) analysis will be conducted on participant samples. Genetic testing (microarray SNP analysis, PCR sequencing, etc.) will be conducted to characterize variants in genes involved in disposition and response of ATX. Some examples of genes that may affect drug disposition and response include, but are not limited to, *CYP2D6*, *CYP2C19*, *ABCB1*, and *SLC6A2*. Genes associated with ADHD phenotype may also be analyzed, especially if ATX response (or lack thereof), is associated with a particular sub-population of individuals with ADHD. Additional testing may be conducted should more information become available regarding genes that may affect the prescribed drug's pharmacokinetic profile, pharmacodynamic characteristics, or clinical outcomes (i.e. safety, efficacy, or toxicity). Information on variants will be analyzed to determine impact on ATX safety, efficacy, or toxicity.

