## 20.2 Sample Size Determination

We hypothesize that there are at least two discrete ATX response phenotypes groups and additionally that these groups may be distinguished by differences in pharmacodynamic markers, and/or baseline patient characteristics. We will use two-sample *t*-tests (if transformed data are approximately Gaussian) or appropriate non-parametric alternatives to test for group differences in baseline and maximal change in DHPG, and a difference in proportions test to assess association between response group and SLC6A2 genotype. To estimate power for these tests we assumed 20% attrition and simulated data for 96 patients. For a 30% response rate among study completers (a conservative estimate),  $\alpha = 0.05$ , and power = 80%, a mean difference of 0.6 SDs between responders and non-responders (eg, on DHPG) was detectable using a one-sided *t*-test. With 120 patients (zero attrition) a 0.5 SD difference was detectable. Depending on the rate and nature of attrition and missing data we will consider non-response weighting or data imputation to reduce estimation bias and improve power. We assessed power for the difference in proportions test based on a 45% probability of a given patient having at least one SLC6A2 lower expression “T” allele (*i.e.*, frequency of SLC6A2 -3081 AT and TT genotypes ~45% based on a minor T allele frequency of 0.061

([http://useast.ensembl.org/Homo\\_sapiens/Variation/Population?db=core;g=ENS G00000103546;r=16:55655604-55706192;v=rs28386840;vdb=variation;vf=109832868](http://useast.ensembl.org/Homo_sapiens/Variation/Population?db=core;g=ENS G00000103546;r=16:55655604-55706192;v=rs28386840;vdb=variation;vf=109832868))).

Assuming attrition of 20% and a response rate of 30%, power was 81% to detect a 0.23 difference in allele frequency between responders and non-responders using a one-sided test. With 120 patients a 0.20 difference was detectable with 80% power.

While these analyses are central to our hypothesis, we recognize that other plasma metabolites or genetic differences may contribute to varying drug response. A target metabolite panel will be assayed in each participant and statistical analyses of these will be analogous to DHPG. A panel of genetic variants will also be analyzed for contribution to variable drug pharmacokinetics, pharmacodynamics, and clinical response in the same manner as the SLC6A2 variant described above.

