Appendix I – Example of neurotransmitters in metabolomics panel

1. 3,4-dihydroxyphenylglycol (DHPG)
2.  $\alpha$ -methyltryptophan
3.  $\alpha$ -tocopherol
4. cysteine
5.  $\delta$ -tocopherol
6.  $\gamma$ -tocopheral
7. guanine
8. guanosine
9. homogentisic acid
10. homovanillic acid
11. hypoxanthine
12. indole-3-acetic acid
13. indole-3-propionic acid
14. kynurenone
15. methionine
16. salicylic acid
17. serotonin
18. tryptophan
19. tyrosine
20. uric acid
21. vanillylmandelic acid
22. xanthine
23. xanthosine
24. 1,3-dimethyl xanthine
25. 1,7-dimethyl xanthine
26. 3-methoxy-4-hydroxyphenyl glycol
27. 4-hydroxybenzoic acid
28. 4-hydroxyphenylacetic acid
29. 4-hydroxyphenyllactic acid
30. 5-hydroxytryptophan
31. 5-hydroxyindoleacetic acid

Appendix J – Study Drug Timeline, a description of drug handling during the ATX PBPK-PD Clinical Outcomes Study

START of Intervention

Designated Study Personnel/PI calculates the initial dose with the iGO-PK model

Study personnel/PI shares the dose calculation with RA/Study coordinator/Designated Study Personnel and Study Physician following the participant

RA/Study coordinator/Designated Study Personnel prepares IDS prescription for 6-8 weeks for Study Physician to sign.

Study Physician signs prescription, scans, and emails back to RA/Study coordinator/Designated Study Personnel

RA/Study coordinator/Designated Study Personnel emails the prescription to IDS to fill and files the original in the subject binder

IDS brings the Rx to the PCRU for Research Visit 2/PK1

At Research Visit 2/PK1

- 1 dose from the prescription is administered to the participant, medication label from IDS is scanned into MAR at dose administration. RN/Designated personnel doses. Topical lidocaine (optional) may also be dispensed.
- PI/Designated Study Personnel teaches family/participant about medication (review prescription details, study booklet calendar, when to contact, anticipated possible side effects, etc)
- PI/Designated Study Personnel give prescription to the family/participant to take home

- PI/Designated Study Personnel write a note in PowerChart documenting this education, the prescription dispensed, and any questions/concerns. Study physician co-signs this note.

At Research Visit 3/PK2

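### Section 20.1 fits ATX-driven models to every panel compound with no meal term and no no-drug comparator, so for compounds that respond to food a meal effect can be credited to ATX

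*Combined protocol and SAP*

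**What the plan says.** **Scope.** Section 20.1 (Pharmacodynamics) says that kin, kout, Imax and IC50 "will be estimated for each metabolite studied using a nonlinear mixed effects model". The Global Neurotransmitter Analysis subsection adds Emax and EC50, says all six "will be determined for all neurotransmitters assessed in the global neurotransmitter panel", and points to Appendix I for the compounds. Imax is defined there as "Maximal fractional inhibition produced by ATX". Section 20.2 adds: "A target metabolite panel will be assayed in each participant and statistical analyses of these will be analogous to DHPG".

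**Panel.** Appendix I gives an example list of 31 compounds. Besides transmitters and their breakdown products it holds three tocopherols, salicylic acid, "1,3-dimethyl xanthine" and "1,7-dimethyl xanthine".

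**Food.** Under Section 11.2, children fast from midnight before Research Visit 2, take ATX, and fast 2 h more. Then: "After this 2-hour mark, the participant is free to eat and drink as desired". Research Visits 3 and 4 follow the same rule, except that evening dosing and the second dose in Study Design 3 need no fast. Meal times and content are documented at all three visits.

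**Covariates and model checks.** The only dietary covariate in Section 20.1 is the Dietary Survey Questionnaire. Section 4.1 ties it to long-term habits, and it is given once, at Research Visit 4. Section 20.1 compares models by sum of squares, log-likelihood, AIC, standard errors and residual distribution. The models it names for these compounds are the indirect model and the Emax model, both driven by ATX.

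**The concern.** Within a sampling day, at least two things change in every child: ATX concentration and feeding state. The planned models contain only the first. The protocol offers little else to separate them. There is no control arm, there is no serially sampled day off drug, and the separate off-drug metabolomics reference is one sample at Research Visit 1. A compound that moves with food will show a post-dose time course that only the ATX term can absorb.

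What is at stake is the meaning of the panel parameters. Section 20.1 compares pharmacodynamic parameters such as Imax and IC50 between responders and non-responders. Section 4.1 wants to relate changes in the neurotransmitter profile under ATX to clinical benefit and toxicity. A parameter labelled as an ATX effect but produced by lunch would mislead both uses. Section 4.1 gives a transporter-based reason to expect an ATX effect on norepinephrine, dopamine, DHPG and related breakdown products. It gives none for tocopherols, salicylic acid or dimethyl xanthines.

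**Working it through.** The plan states no figure on this point, so there is none to reproduce.

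**1. Samples after eating is allowed** (times from Section 11.2)

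- Study Design 2: 0.5, 0.75, 1, 1.5, 2 | 3, 4, 6, 8, 10, 12 h. After 2 h: 6 of 11.
- Study Design 1, Research Visit 2: the same 11 plus 16, 20, 24, 48, 72 h. After 2 h: 6 + 5 = 11 of 16.
- Study Design 1, Research Visits 3 and 4: the same 11 plus 16, 20, 24 h. After 2 h: 6 + 3 = 9 of 14.

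**2. What the model can do with a food response.** Equation A is not in the text available, so two standard forms were considered, with I(C) = Imax·C/(IC50 + C):

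- production inhibited: dR/dt = kin·(1 − I) − kout·R. R can only fall from baseline and recover.
- loss inhibited: dR/dt = kin − kout·(1 − I)·R. R rises after the dose. Stimulation of production also lets R rise.

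At Research Visit 2 the pre-dose sample is fasted and at zero ATX. A compound that food raises is as low there as at the ATX peak. Production inhibition describes that pattern poorly. A form that lets R rise can follow it.

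**3. How often a false ATX effect appears.** Everything here except the sampling times is an assumption: 96 children, Study Design 2 times, ATX half-life about 4 h, 20% residual CV, no ATX effect, and a sustained food rise of 5%, 10% or 20% after 2 h. Three separate implementations of a simplified turnover fit gave these percentages of trials with a false effect:

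| Form | First | Second | Third |
|---|---|---|---|
| Lets compound rise | 83, 100, 100% | 87–100% | 90–100% |
| Production inhibited | 0–13% | 1, 9, 43% | 1–8% |

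Triples are for rises of 5, 10 and 20%. With no food effect, the rising form gave 3% in the first implementation.

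**4. Whether a meal term removes it.** This was a separate simulation, again on assumed values: 24 children, Study Design 2 times, ATX half-life about 3.5 h, Cmax about 400 ng/mL, 12% residual error, and no ATX effect. Formation changed by +50% or −30% for 2 h after each of three meals (about 2.1–2.5, 5.5–6.5 and 9.5–10.5 h). Fits were pooled, not full mixed-effects. Apparent inhibition at 400 ng/mL is Imax·400/(IC50 + 400); for example, 1.00·400/(2652 + 400) = 0.13. The AIC gain is AIC without ATX minus AIC with ATX. The ATX term adds two parameters, a penalty of 2·2 = 4, so −4.0 means no improvement in fit.

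| kout (/h), meal effect | Form inhibits | No meal term: inhibition, AIC gain | Meal term: inhibition, AIC gain |
|---|---|---|---|
| 0.3, +50% | production | 13%, 25.6 | 0%, −4.0 |
| 0.3, +50% | loss | 38%, 163.0 | 3%, −3.6 |
| 0.3, −30% | production | 30%, 59.4 | 0%, −4.0 |
| 0.3, −30% | loss | 9%, 14.1 | 5%, −2.9 |
| 1.0, +50% | production | 11%, 16.0 | 4%, −1.7 |
| 1.0, +50% | loss | 35%, 134.8 | 0%, −4.0 |
| 1.0, −30% | production | 23%, 85.8 | 0%, −4.0 |
| 1.0, −30% | loss | 8%, 9.2 | 3%, −2.1 |

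Without the meal term AIC preferred a false ATX effect in 8 of 8 fits; with it, in 0 of 8. Each data set was simulated once, so this shows the mechanism and is not a rate. In four control fits with no meal effect and no meal term, three showed no ATX effect and one a small chance effect (8%, AIC gain 8.0). One control fit with the meal term returned 49% inhibition although AIC did not support the ATX term (−3.8). An unsupported estimate can therefore still look large.

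**The case against.** A reader might infer that meal effects will be estimated as ATX inhibition, because children are fasted while ATX peaks and fed while it falls. The documents do not support that. The fasted, zero-ATX pre-dose sample at Research Visit 2 contradicts that shape, the production-inhibition form mostly rejects a food rise, and an Emax model is also planned. Nor should false-positive rates from a direct concentration–effect fit, which has no kin or kout, be carried over to the turnover model.

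A reader might also multiply the Appendix I list by six parameters. But the list is labelled an example, Section 4.1 says approximately 30 compounds, and Imax/IC50 and Emax/EC50 belong to alternative models.

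Further points are fair:

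- Standard errors are among the planned checks and would expose many unstable values. In the table above, 5 of the 8 IC50 estimates without a meal term sat at the search limits (1 or 3,000 ng/mL).
- Responders and non-responders dosed in the morning follow the same fasting rule, so a shared meal artefact does not by itself create a group difference.
- The baseline metabolomic comparison of responders with non-responders does not need Imax or IC50.
- Nothing here shows that DHPG itself is distorted.

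These limit the size and reach of the problem. They do not remove it. Every model named for these compounds is driven by ATX, so the planned comparison can choose between two wrong explanations. A no-drug model alone would not be enough either, since a meal signal can beat it. A survey of long-term diet cannot describe change within a day.

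**Conclusion.** The concern holds in a limited form. For panel compounds that respond to meals, the plan as written can credit a meal effect to ATX. Whether it shows as inhibition or stimulation, and how large it is, depends on the compound and on Equation A.

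Under the assumed values a false ATX effect is close to certain when the model lets the compound rise: about 90–100% of trials, with a lowest result of 83%. It is mostly uncommon when ATX inhibits production: generally under about 10%, but 43% in one implementation at a 20% rise. These figures rest on assumed food effects, residual error and simplified fits, cover Study Design 2 sampling only, and do not estimate the bias in this trial. That the named compounds are mainly dietary is general knowledge, not protocol text.

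The change should be made. It concerns a secondary analysis and can be repaired before analysis from data already recorded.

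**What to change.** In Section 20.1:

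1. For each compound, fit a no-drug turnover model and an ATX model, both with a time-varying meal term built from the recorded meal times. Allow the ATX effect in either direction only with that term present; without it, the added freedom raises the false-positive rate.
2. Report Imax/IC50 or Emax/EC50 only where the ATX model is supported over the no-drug model and the standard errors are acceptable. Otherwise state that no ATX effect was supported.
3. Treat tocopherols, salicylic acid and the dimethyl xanthines as food and caffeine markers, and do not fit ATX models to them.
4. As a sensitivity analysis, use only the pre-meal samples from 0 to 2 h, excluding children given food earlier. This will be imprecise for compounds with slow turnover.

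The cost is SAP wording, modest extra modelling and fewer reported parameters. Section 12.0 says only a subset of the data goes into the study database, so the meal records should be added to that subset. A meal term does not remove time-of-day effects, which the design cannot separate without a serially sampled off-drug day; the report should say so.

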#### Pupillometry Analysis:

Changes in performance during Posner Cuing Task will be measured as a function ATX exposure and  $C_{max}$  concentrations. Pupil size will be measured during two types of activities: localization and discrimination tasks. Pupil size differences during localization tasks report on the individuals' baseline (tonic) release of norepinephrine. This corresponds to endogenous, or volitional attention. Pupil size differences during discrimination tasks is a composite of the individuals' baseline (tonic) and situational (phasic) release of norepinephrine. Currently it is unclear whether tonic, phasic, or both are impaired in individuals with ADHD.

Cardiovascular Marker Analysis:

Changes in heart rate will also be measured as a function ATX exposure and  $C_{max}$  concentrations. One side effect of ATX that is directly related to the pharmacodynamics of the drug is an increased heart rate due to increased concentration of norepinephrine in blood. We would like to understand the extent of this side effect as a function of increased systemic ATX exposure and  $C_{max}$ . By studying these two components, we will be able to distinguish ATX drug action in central and peripheral nervous systems.

Pharmacodynamic Changes Correlated with change in NICHQ Vanderbilt Assessment Scales:

All changes markers of pharmacodynamic action will be correlated with whether a child is classified as a responder or non-responder; and tolerant or intolerant (see Clinical Outcomes below for details). Extent of adherence will be used as a confounding factor in both of these analyses.

Clinical Outcomes:

Determine and document participant response to ATX therapy:

- Responders will be defined as:
  - Participants, who after approximately 18 weeks of continuous treatment with ATX, demonstrate  $\geq 40\%$  reduction of baseline ADHD symptom score;
  - OR the Clinical Global Improvement rating is 1 or 2 (Very Much Improved or Much Improved).
- Non-responders will be defined as:
  - Participants, who after approximately 18 weeks of continuous treatment with ATX, demonstrate  $< 40\%$  reduction of baseline ADHD symptom score, AND the Clinical Global Improvement score  $\geq 3$ .
  - Participants who discontinue ATX prior to the planned end of study (18 weeks) due to perceived lack of efficacy despite dose escalation.

Determine and document participant tolerance of ATX therapy:

- ATX intolerant participants are:
  - Participants who present with side-effects that significantly interfere with daily functioning or outweigh therapeutic benefit (CGI Efficacy Scale categorization)
  - Participants who must discontinue ATX for any of the following reasons: AST or ALT three times the upper limit of normal (ULN) for age, alkaline phosphatase five times the ULN, total bilirubin two times ULN, QT prolongation or dysrhythmia, hypertension (systolic or diastolic BP above 95% for age), tachycardia (HR above 95% for age)

Parent and teacher responses for the NICHQ Vanderbilt Assessment Scales will be obtained at baseline and  $\pm$  2 weeks of 6-week Visit with Study Physician, 12-week Visit with Study Physician, and 18-week Visit with Study Physician. If questionnaires are returned outside of this window, or are unreturned, these will be considered, "missing data." Determination of response, i.e. responder vs. non-responder, will be done using parent responses to questionnaires. Teacher response to questionnaires will also be analyzed to evaluate symptom reduction in a secondary setting. Partial return of teacher questionnaires are still useful in that these data may be used to correct for bias in parental response.

Questionnaires conducted at baseline and at either 18-week visit with Study Physician or a Research Visit will be analyzed for change pre- and post-intervention. These include: BRIEF – parent, SCT, SCARED, CBCL, and School Intervention Questionnaire.

Statistical analyses of clinical response in the population studied will be performed by The Division of Health Services and Outcomes Research at the Children's Mercy Hospital, Kansas City, MO. SAS version 9.4 (SAS, Cary, NC, USA) and R (The R Foundation) will be used to determine if ATX responders and non-responders can be differentiated by a subset of patient specific covariates.

Variables that will be included in this analysis are data collected at the patient's initial clinic visit: DHPG, *SLC6A2* genotype, ADHD subtype, ADHD severity, co-morbid anxiety or oppositional defiant disorder, age, and gender. Predictive power of classification models will be assessed by computing the area under the receiver operating characteristic curve and/or by k-fold cross-validation. Two-sample t-tests or non-parametric alternatives will be utilized to test for group differences in percent decrease in DHPG and a differences in proportions test will be used to assess the association between response and *SLC6A2* genotype. In addition, global metabolomic analyses will be conducted to determine whether non-responders and responders are intrinsically different in their biochemical make-up. This will further understanding of how differences in

response phenotype could be a result of different biological pathway involvement in ADHD. Digital maps will be constructed for partial least square-discriminant analysis (PLS-DA) models with prior knowledge of which volunteers were categorized as responders and non-responders. The variable influence on the projection (VIP) parameter will be used to identify which metabolites (i.e. pathways) are the most predictive of differentiating between the responder and non-responder populations. Analyses will also be conducted to determine mechanistic reasons for why certain individuals are non-responders or responders. Changes in pharmacodynamic endpoints will be compared between responders and non-responders. Specifically pharmacodynamic parameters such as  $I_{max}$ ,  $IC_{50}$ , differences in pupil diameter changes in localizations and discrimination tasks, and overall change in DHPG will be compared between the two populations using MANOVA and/or appropriate two-sample test.

ATX pharmacodynamic data for each *SLC6A2* activity group will be examined using standard descriptive statistics. Analysis of variance will be used to compare parameters between pre-defined genotype populations followed by application of the appropriate parametric or non-parametric post-hoc test to determine where inter-group differences occur. Linear and non-linear least squares regression analysis will be used to examine the correlation between DHPG fitted parameters and changes in eye-tracking and pupillometry differences in *SLC6A2* genotype groups. Univariate analysis of variance, nonlinear regression and analysis of covariance will be used to evaluate the relationship between demographic variables (alone or in combination) with corresponding pharmacodynamic parameter estimates. All analyses will be performed in SPSS version 11.5 (SPSS, Chicago, IL) with the significance limit set at  $\alpha=0.05$ . A sample size of 120 was deemed reasonable with the volume of patients being referred to the ADHD sub-specialty over a four year period. Powering of statistical tests was done assuming 20% attrition and data simulated for 96 patients. Assuming that 30% of the participants completing the study are categorized as responders, an  $\alpha = 0.05$ , and power = 80%, a mean difference in covariates assessed of 0.6 standard deviations is detectable with a one-sided t-test. With zero attrition, the mean detectable difference in covariates of interest drops to 0.5 standard deviations.

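### Pharmacodynamic markers are tied to clinical outcome only through binary classes; a continuous Vanderbilt analysis, which a section title promises, is never specified

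*Combined protocol and SAP*

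**What the plan says.** The second primary objective (Section 2.1) and Hypothesis 2 (Section 2.2) concern how pharmacodynamic (PD) markers relate to clinical response. Section 20.1 gives the analysis under the title "Pharmacodynamic Changes Correlated with change in NICHQ Vanderbilt Assessment Scales". The text below that title says: "All changes markers of pharmacodynamic action will be correlated with whether a child is classified as a responder or non-responder". The same sentence goes on to tolerant or intolerant status, and adherence is treated as a confounder.

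Later in Section 20.1, "Changes in pharmacodynamic endpoints will be compared between responders and non-responders". Imax, IC50, pupil changes and DHPG change "will be compared between the two populations using MANOVA and/or appropriate two-sample test". Section 20.2 powers only group tests of this kind.

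Response is a composite, set out under Clinical Outcomes in Section 20.1:
- Responder, first route: "Participants, who after approximately 18 weeks of continuous treatment with ATX, demonstrate" a fall of at least 40% from the baseline symptom score.
- Responder, second route: "OR the Clinical Global Improvement rating is 1 or 2 (Very Much Improved or Much Improved".
- Non-responder: neither criterion met at about 18 weeks. The class also takes in "Participants who discontinue ATX prior to the planned end of study (18 weeks) due to perceived lack of efficacy despite dose escalation".

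Section 20.1 bases response on the parent questionnaire, which is scheduled at baseline and at the 6-, 12- and 18-week visits.

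**The concern.** The section title and the text under it describe different analyses. The other places where a continuous analysis might be found do not supply one:
- The regressions in Section 20.1 relate markers to drug exposure, patient covariates, genotype or each other, never to a symptom score.
- Teacher-rated symptom reduction and pre/post change in the other questionnaires are analysed, but are not linked to a marker.
- The analysis-population list also names adherence (three levels) and adverse-event reporting as clinical outcomes. It gives no method that relates either to a marker.

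At stake is the power of the analysis that answers a primary objective, using scores the study already collects. There is also a gap in coverage. Children seen only up to Research Visit 3 and the 6-week visit count toward the 120 (Section 8.2) and enter the PD-linked outcome analysis (Section 20.1). A child who leaves after week 6 for a reason other than lack of efficacy fits neither response class, although a week-6 score may exist.

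**Working it through.** **Inputs (Section 20.2).** 30% responders; α = 0.05, one-sided; 80% power; 96 patients after 20% attrition, or 120 with none; stated detectable differences of 0.6 SD and 0.5 SD.

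**1. The plan's own figures.** Detectable difference ≈ (1.645 + 0.842) × √(1/n₁ + 1/n₂).
- N=120 (36/84): 2.487 × 0.1992 = 0.495 SD, or 0.498 with the t distribution. Power at 0.5 SD is 80%. This reproduces.
- N=96 (29/67): 2.487 × 0.2223 = 0.553 SD, or 0.557 with t. This matches 0.6 after rounding to one decimal. Power at exactly 0.6 SD is 85%.

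**2. Information kept by the split.** Assume one normal outcome, a linear association with the marker, and a cut on Vanderbilt alone. The share kept is φ(z)² / [p(1−p)]. At p = 0.30, φ(z) = 0.3477, giving 0.1209 / 0.21 = 0.576, a loss of 42%. In effective numbers, 120 × 0.576 ≈ 69 and 96 × 0.576 ≈ 55.

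| Response rate | Loss |
|---|---|
| 20% | 51% |
| 30% | 42% |
| 40% | 38% |
| 47% (rate cited in Section 3.1) | 36% |
| 50% | 36% |

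**3. Power under the same assumptions, every score present.** Convert the group difference d to a point-biserial correlation, d√(p(1−p)) / √(1 + d²p(1−p)). Multiply by √(p(1−p)) / φ(z) to get the underlying correlation ρ. Continuous power is Φ(atanh(ρ)√(N−3) − z_α).
- d = 0.5, N=120: 0.223 becomes ρ = 0.294. Then atanh(0.294) × √117 ≈ 3.28. One-sided power is Φ(3.28 − 1.645) ≈ 95%, against 80% for the split. Two-sided it is Φ(3.28 − 1.96) ≈ 91%, against 70%.
- d = 0.6, N=96: 0.265 becomes ρ = 0.349. Then atanh(0.349) × √93 ≈ 3.52. One-sided power is about 97%, against 85%.

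Simulation of 20,000 trials per setting, at ρ = 0.29 and 0.347, agreed: 94% against 79% at N=120, and 97% against 84% at N=96.

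**4. Composite rule.** Suppose the marker acts through Vanderbilt only and the two criteria together give 30% responders. The loss is then 46% if Vanderbilt and the global rating correlate at 0.9, and 62% at 0.5. These correlations are assumptions; the documents give none.

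**5. Two true classes (30/70), marker following class.** Compare the squared correlation of each outcome with true class. For the continuous score this is 0.21D² / (1 + 0.21D²), where D is the class separation in within-class SDs. The split's values were simulated.

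| D | Continuous | Split | Split ÷ continuous |
|---|---|---|---|
| 1 | 0.173 | 0.129 | 0.74 (26% loss) |
| 2 | 0.457 | 0.442 | 0.97 (3% loss) |
| 3 | 0.654 | 0.735 | 1.12 (split better) |
| 4 | 0.771 | 0.904 | 1.17 (split better) |

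**The case against.** The best defence is that the class analysis follows from the study's hypothesis. Section 20.2 posits at least two discrete response groups, Section 3.1 gives the background for them, and Section 3.3 says response criteria were set in advance by the clinical team. Step 5 shows that with well-separated classes the split is the more efficient analysis. This stands, and it is why the responder comparison should stay. It does not justify relying on that comparison alone, because discreteness is something the study sets out to examine.

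A reader might infer several stronger points that the documents do not support:
- *That 42% of the information is lost outright.* That figure needs a single normal outcome, a cut on Vanderbilt alone and 30% responders. The plan's rule adds the global rating and a discontinuation criterion, and its hypothesis is not a single normal outcome.
- *That children with 39% and 0% reductions are treated alike.* A child at 39% with a global rating of 2 is a responder; a child at 0% with a rating of 4 is not.
- *That the split gains nothing.* It keeps children who stop for lack of efficacy in the analysis without a week-18 score. A regression on week-18 score alone would lose or have to impute them, and that loss is related to outcome. The power figures in step 3 assume no such loss.
- *That response is the only class used.* Tolerance is used too, and it is also binary.

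**Conclusion.** The point holds in a conditional form. Every specified analysis that links a PD marker to clinical outcome uses a binary class, and the title in Section 20.1 promises something its text does not deliver. The possible power gain is substantial if response is graded (about 80% to 95% one-sided at N=120, given the assumptions in steps 2 and 3). It is small or negative if response is clearly two-class. The study does not know in advance which applies, so specifying both analyses is the safer plan. A reader might also conclude that the responder comparison should become secondary. The documents do not require this: it is a deliberate clinical choice, and which analysis leads is a trade-off. This is an inexpensive improvement to an objective worded as exploratory, not a fault that invalidates the planned comparison.

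**What to change.** Keep the responder/non-responder comparison. Beside it, prespecify in Section 20.1 a model of parent Vanderbilt score on each key PD marker (DHPG change and pupil change), adjusted for baseline score, with adherence as a covariate.

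A mixed model over weeks 6, 12 and 18 is preferable to a week-18 regression. Partial completers and children who stop early then contribute whatever post-baseline scores they have.

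State which PD visit is paired with the scores. Markers are measured at the research visits, not at weeks 6, 12 and 18. Research Visit 3 may fall at any time from two weeks of routine dosing until before the 18-week visit, and Research Visit 4 comes after that visit (Section 11.1).

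The cost is SAP wording, one further model per key marker, and a slope to report beside the group difference. No new data are needed. The mixed model assumes scores are missing at random for children without a week-18 value. That assumption should be stated and reconciled with the weighting or imputation that Section 20.2 leaves open.
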